- An anthracycline; either daunorubicin , idarubicin or mitoxantrone at standard doses daily for 3 days, starting on day 1.

The second induction will consist of dose-adjusted high dose Ara-C alone (1-1.5grm/m² Q12 hrs on day 1, 3, and 5, per standard of care). The timing for initiation of the second induction depends upon results of marrow done 14-21 days after the first induction according to standard of care practice.

- Patients who do not achieve remission at the conclusion of 2 inductions will be considered screen failures and offered alternative therapies.

Consolidation:

- Omacetaxine 1.25 mg/m² sub-cutaneously twice daily for 5 consecutive days every 28 (\pm 8) days for a total of 3 cycles.

Maintenance:

- Subjects in continuous remission after 3 cycles of consolidation with omacetaxine will receive maintenance omacetaxine 1.25mg/m² twice daily for 3days, every 28 days, for up to 6 cycles.

Sample size and patient selection:

- **Screening:** 45 patients with newly diagnosed, untreated AML eligible for induction chemotherapy. Patients who received 1-2 cycles of hypomethylating therapy for cytoreduction are also eligible.
- **Consolidation/maintenance:** 15 patients in first complete remission after 2 inductions.

Assessment of response:

- Bone marrow biopsy and aspirate will be obtained at day 14-21 of the 1st cycle, and at day 28 or at count recovery, whichever occurs first.
- Prior to each consolidation cycle, responses will be evaluated with a complete blood count (CBC) and bone marrow aspiration/biopsy to document continued remission.
- Bone marrow aspirate to confirm continuous remission will be obtained every 3 months during maintenance, and as clinically indicated thereafter.

Statistical Methods:

- This study is an open label, pilot study. Continuous data will be described using descriptive statistics (n, mean, median, minimum, and maximum) while discrete data will be described using frequency counts and percentages.

Time line: 2-3 years, based on previous accrual in the target population.

1. BACKGROUND:

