Cycle #1: Cytarabine at $100\text{mgm}^2/\text{dose}$ via continuous infusion daily for 7 days, starting on day 1.

Daunorubicin, idarubicin, or mitoxantrone at standard dosing daily for 3 days, starting on day 1.

Cycle #2: Cytarabine 1- $1.5\text{gm}/\text{m}^2/\text{dose}$ IV twice daily on days 1, 3 and 5.

- Study specific evaluations during induction (See **Appendix D**)

B. Consolidation:

- Omacetaxine 1.25 mg/m² sub-cutaneously twice daily for 5 consecutive days every 28 (\pm 8) days for 3 cycles, provided that prior to the next planned treatment cycle, the patient's absolute neutrophil count (ANC) recovers to $\geq 1 \times 10^9/L$ and the platelet count recovers to $\geq 100 \times 10^9/L$. Patients with history of or suspected MDS prior to AML who fail to recover their ANC and platelets after induction chemotherapy, may start omacetaxine upon recovery to baseline pre-AML ANC and platelet count. Omacetaxine can be administered at Emory/Winship Cancer Institute or by self- injection at home.
- Evaluations during consolidation (see **Appendix E**)

C. Maintenance:

- Patients in continuous remission after 3 cycles of consolidation will receive maintenance omacetaxine 1.25mg/m² twice daily for 3 days, every 28 days for up to 6 cycles, provided that prior to the next planned treatment cycle, the patient's absolute neutrophil count (ANC) recovers to $\geq 1 \times 10^9/L$ and the platelet count recovers to $\geq 100 \times 10^9/L$. Patients with history of MDS prior to AML who fail to recover their ANC and platelets after induction chemotherapy, may start omacetaxine upon recovery to baseline pre-AML ANC and platelet count. Omacetaxine can be administered at Emory/Winship Cancer Institute or by self- injection at home.
- Evaluations during maintenance (see **Appendix F**)

D. Supportive Care (these guidelines are not protocol requirements as these as standard of care practices):

- Standard anti-microbial prophylaxis will be instituted for every patient enrolled in this study. Suggestions include: anti-viral (acyclovir or valacyclovir), anti-bacterial (fluoroquinolone, doxycycline, or standard alternative) and anti-fungal (azole or micafungin) prophylaxis will be initiated at the onset of neutropenia according to our institutional standard. Patients experiencing fever will be treated according to institutional practice, with blood cultures, imaging of suspected areas of infection, and empiric antibiotics targeted at the suspected cause of fever.

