Toxicities will be monitored by history, physical examination, and laboratory monitoring (CBC, serum chemistries to include renal and liver function tests) weekly during consolidation and monthly during maintenance according to standard of care (Appendices D-F). Toxicity will be assessed according to the NCI Common Toxicity Criteria Version 4.0 (available at the NCI web site <http://ctep.cancer.gov/reporting/ctc.html>). Adverse events will be monitored on an ongoing basis. No AEs will be collected during the screening period (the time from diagnosis to completion of the standard of care inductions).

3.3.4 Dose Modifications and Stopping Rules:

A. Omacetaxine

- ***Hematological toxicity:***

- The following table summarizes dose adjustments for hematological toxicity during consolidation and maintenance with Omacetaxine and are based on time to count recovery to < grade 2 hematological toxicity. Hematologic toxicity only refers to WBC/neutrophils and platelets and not hemoglobin/hematocrit, given that anemia is expected and may not resolve after chemotherapy regardless of AML-status. Dose-reductions and delays do not apply to anemia.

Time to resolution to < grade 2 hematologic toxicity (days)	Action 1	Action 2: Hematologic toxicity after 1 st dose reduction
≤ 36	No dose reduction	No dose reduction
> 36 and < 50	20% dose reduction, i.e. omacetaxine 1.25 mg/m ² sub-cutaneously twice daily for 4 days during consolidation, or 1.25mg/m ² twice daily for 3 days during maintenance	Additional 25% dose reduction, i.e. omacetaxine 1.25 mg/m ² sub-cutaneously twice daily for 3 days during consolidation, or 1.25mg/m ² twice daily for 2 days during maintenance
> 50	Perform bone marrow aspirate and biopsy. If relapse – patient will be taken off study. If hypoplastic marrow (cellularity < 10%), reassess after 2 weeks. If recovery achieved within 2 weeks post-marrow assessment, resume omacetaxine after 60% dose reduction; i.e. omacetaxine 1.25 mg/m ² sub-cutaneously twice daily for 3 days during consolidation, or 1.25mg/m ² twice daily for 2 days during maintenance If no recovery 2 weeks post-marrow assessment, patient will be taken off study.	No further dose reduction. Patient will be taken off study

- ***Non-hematological toxicity:***

- Patient with grade III-IV non-hematological toxicity (deemed at least “possibly” related to omacetaxine) will have study drug held until toxicity has recovered to grade 1 or less. Treatment may resume after 20% dose reduction.

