- Patient who develop grade II non-hematological toxicity that is related to omacetaxine will have study drug held at treating physician’s discretion, until toxicity has recovered to grade 1 or less. Treatment will resume after 20% dose reduction.
- If grade III-IV non-hematological toxicity recurs after dose-reduction, the patient will discontinue protocol therapy.
- If grade III-IV non-hematological toxicity does not resolve to grade 1 or less by day 36 of therapy with omacetaxine, then patient will be taken off study.

B. Cytarabine

The following guidelines are not protocol requirements given that patients are receiving Institutional standard induction.

Doses of cytarabine can be **reduced** during the second induction in cases of decrease in the calculated creatinine clearance $> 20\%$ but less than 50% . HiDAC will be discontinued and patient taken off study if neurotoxicity occurs at any time during HiDAC therapy.

C. Daunorubicin, Idarubicin, or mitoxantrone

The following guidelines are not protocol requirements given that patients are receiving Institutional standard induction.

- Drug will be withheld and patients will be withdrawn from the study, if they experience a clinically significant decrease in left ventricular ejection fraction, leading to a diagnosis of symptomatic congestive heart failure.
 - Adjustments for hepatic and renal dysfunction will conform to recommendation from the package inserts and standard practice.

D. Stopping Rules

- Omacetaxine will be **discontinued** in cases of
 - Delay in recovery of ANC to $\geq 1,000/\text{mcL}$ and platelets to $\geq 100,000/\text{mcL}$ or to baseline ANC and platelets (for patients with history of underlying MDS) after 50 days.
 - Grade III-IV irreversible non-hematological toxicity attributable to omacetaxine
 - Recurrence of grades III-IV non-hematological toxicities after dose-reduction.
 - Recurrent leukemia.
 - Patient’s or treating physician’s request.

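### Section 3.3.4 A: the first-step 20% dose reduction in maintenance is written as the full maintenance schedule, so the dose is not reduced at all

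*Combined protocol and SAP*

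**What the plan says.** **Full maintenance dose.** The Synopsis sets maintenance omacetaxine at 1.25 mg/m² "twice daily for 3days, every 28 days, for up to 6 cycles". Section 3.3.1 C repeats it: "twice daily for 3 days, every 28 days for up to 6 cycles".

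**Hematological dose table (Section 3.3.4 A).** Adjustments are "based on time to count recovery to < grade 2 hematological toxicity".

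- Recovery after more than 36 and before 50 days, first occurrence: a 20% reduction, given as 4 days in consolidation or 1.25 mg/m² "twice daily for 3 days during maintenance".
- Same delay after a first reduction: "Additional 25% dose reduction", given as 3 days in consolidation or 2 days in maintenance.
- More than 50 days, first occurrence: a marrow is done. For a hypoplastic marrow with later recovery the table says "If recovery achieved within 2 weeks post-marrow assessment, resume omacetaxine after 60% dose reduction", given as 3 days in consolidation or 2 days in maintenance.
- More than 50 days after a first reduction: the patient comes off study.

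**Non-hematological rules (same section).** For grade III-IV toxicity: "Treatment may resume after 20% dose reduction". For grade II: "Treatment will resume after 20% dose reduction". Neither gives a schedule.

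**Stopping Rule D (Section 3.3.4).** Omacetaxine is discontinued if, after 50 days, ANC has not reached 1,000/mcL and platelets 100,000/mcL, or baseline values in patients with underlying MDS.

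**The concern.** The first-step reduction in maintenance uses the same dose, frequency and number of days as the unreduced schedule. A patient whose counts recover late is re-treated at full dose under an instruction labelled a reduction. Safety and tolerability of maintenance is one of the two primary objectives, and the day count is what a site or a self-injecting patient will follow.

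The error also carries into other rules:

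- **The second column of the table** applies after a first dose reduction. A maintenance patient given the empty first step counts as already reduced. If the next delay exceeds 50 days, that patient goes off study and loses the marrow assessment and possible restart at 2 days, without ever having had a lower dose.
- **The non-hematological rules** ask for 20% with no schedule. This table entry is the only text that turns 20% into maintenance days. A clinician relying on it would rechallenge at full dose after grade III-IV toxicity, and a recurrence after that supposed reduction ends protocol therapy.
- **Section 6** defines DLT by pointing back to Section 3.3.4, so unclear rules there also blur what counts as a DLT.

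Separately, Stopping Rule D and the row for more than 50 days disagree. Take a patient who meets neither recovery test after day 50, has a hypoplastic marrow, and recovers within 2 weeks of it. The table lets this patient resume; Rule D discontinues. The two also use different recovery tests, only Rule D makes the MDS-baseline exception, and no text says which governs.

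**Working it through.** **Inputs.** 1.25 mg/m² per injection, twice daily, in every cell of the table. Full schedules: 5 days in consolidation (Section 3.3.1 B) and 3 days in maintenance (Section 3.3.1 C and Synopsis).

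**Formulas.** Dose per cycle = 1.25 × 2 × days = 2.5 × days (mg/m²). Reduction = 1 − (new dose ÷ reference dose).

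**Step 1: reproduce the consolidation entries.** Full dose is 2.5 × 5 = 12.5. First step is 2.5 × 4 = 10.0, and 1 − 10.0/12.5 = 20%, as stated. Second step is 2.5 × 3 = 7.5, and 1 − 7.5/10.0 = 25%, as stated. This confirms how the percentages were meant to work.

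**Step 2: apply the same arithmetic throughout.**

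| Step | Phase | Dose before → after (mg/m² per cycle) | Stated | Actual |
|---|---|---|---|---|
| First step, > 36 and < 50 days | Consolidation | 12.5 → 10.0 | 20% | 20% |
| First step, > 36 and < 50 days | Maintenance | 7.5 → 7.5 | 20% | **0%** |
| Second step | Consolidation | 10.0 → 7.5 | 25% | 25% |
| Second step | Maintenance | 7.5 → 5.0 | 25% | 33% |
| > 50 days, resumed | Consolidation | 12.5 → 7.5 | 60% | 40% |
| > 50 days, resumed | Maintenance | 7.5 → 5.0 | 60% | 33% |

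A true 60% cut would be 0.4 × 12.5 = 5.0 in consolidation and 0.4 × 7.5 = 3.0 in maintenance. The 60% figure matches the share of the consolidation dose kept (7.5/12.5), not the share removed.

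**Step 3: size of the first-step error.** The label implies 0.80 × 7.5 = 6.0 mg/m². The written schedule exceeds that by 1.5 mg/m² per cycle, and 7.5/6.0 = 1.25, so it is 25% above the labelled dose. If the first delay follows maintenance cycle 1 and no further delay occurs (an assumption), up to 5 cycles are affected: 5 × 1.5 = 7.5 mg/m², equal to one full maintenance cycle.

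**Step 4: is a 20% step available?**

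- Keeping 1.25 mg/m² injections: 6.0/1.25 = 4.8 injections, so not exactly. Five of six gives 6.25 mg/m², and 1.25/7.5 = 16.7%.
- Dropping a whole day: 5.0 mg/m², 33.3%.
- Changing the injection: 1.0 mg/m² twice daily for 3 days = 6.0 mg/m², exactly 20%.

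**Step 5: could the baseline be misread?** The 3-day schedule appears in two separate places, so a text-extraction fault is unlikely. A 4-day baseline, which appears nowhere, would make 3 days a 25% cut, still not 20%.

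**Step 6: row boundaries.** The rows cover up to 36 days, more than 36 and fewer than 50, and more than 50. Exactly 50 days is in none of them.

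**The case against.** The mismatch itself is not open to dispute; the case on the other side is about how much it matters.

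- **The five-cycle excess arises only when no further delay occurs**, that is, in a patient whose counts are tolerating 3 days. A patient with a second delay in the same range moves to 2 days, a real 33% cut, after one unreduced cycle. This stands. The five-cycle figure is an upper bound, not a typical harm. It does not cover a non-hematological 20% reduction.
- **Other safeguards limit harm.** Each cycle requires count recovery, the physician may stop the drug, and a maintenance cycle is already 40% below a consolidation cycle (7.5 against 12.5 mg/m²). Waiting until at least day 37 lowers that cycle's dose per unit time by at least 24% (1 − 28/37). This also stands, but none of it lowers the dose given in later cycles. Blood-count monitoring is a weaker safeguard than it looks: Appendix F has it weekly at first and then optionally every other week, while Section 3.3.3 says monthly.
- **Few patients will be affected.** Only 15 are planned for omacetaxine, fewer will reach maintenance, and fewer still will have a first delay of 37 to 49 days. True, and the number is unknown.
- **The schedule, not the percentage, may be what was intended**, since the table cuts whole days and one day is 33% of maintenance. Possible. In that case the cell should say that no reduction applies; calling it 20% is still wrong.
- **The 25%, 60% and day-50 faults are minor**, because an explicit schedule accompanies each label and the gap is one day. Agreed; they are ranked accordingly.

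**Conclusion.** The concern holds. In maintenance the first-step reduction is stated as 20% and delivers 0%: 7.5 mg/m² per cycle before and after. This follows directly from the Synopsis, Section 3.3.1 C and the table in Section 3.3.4 A, and rests on no outside assumption. It must be fixed, because following the table gives the full dose under a rule meant to lower it.

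The excess of 1.5 mg/m² per cycle takes the 20% label as the intent. The cumulative 7.5 mg/m² is an upper bound that also assumes a first delay after cycle 1 and none later.

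The Rule D conflict should be fixed too, though it reaches only a small group. Its effect on feasibility or DLT counts is not quantified: that depends on whether reduced-dose cycles count as full delivery and whether a Rule D discontinuation is a DLT, and Section 6 settles neither. The remaining label errors and the day-50 gap are minor.

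**What to change.** 1. **Maintenance first step.** Replace it with a real reduction, for example 5 of 6 injections at 1.25 mg/m² (6.25 mg/m², labelled 17%), or 1.0 mg/m² twice daily for 3 days (6.0 mg/m², exactly 20%) if the team prefers full treatment days. State that the same schedule is the maintenance step under the non-hematological rules, and amend their 20% wording if the 17% option is chosen.
2. **Maintenance second step.** Keep 2 days (5.0 mg/m²), 33% below full dose. Label it as a further 20% if the first step is 6.25 (1.25/6.25), or a further 17% if it is 6.0 (1.0/6.0).
3. **Row for more than 50 days.** Relabel the 60% as 40% for consolidation and 33% for maintenance. Change the boundary to 50 days or more, and use the same boundary in Rule D.
4. **Rule D.** Make it follow the table: discontinue if counts have not recovered 2 weeks after the marrow, or on a repeat delay of 50 days or more after a dose reduction. Alternatively, delete the option to resume from the table. Use one recovery test in both places, including the MDS-baseline exception.

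The clinical team should confirm the dose values. The cost is a protocol amendment to one table, one stopping-rule bullet and the non-hematological reduction wording, with no extra patients, visits or procedures.

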2. STUDY OBJECTIVES

Primary Objectives:

- To assess the safety and tolerability of delivering omacetaxine for consolidation in adult patients age 55 and older with acute myelogenous leukemia (AML) in first complete remission following induction chemotherapy.
- To assess the safety and tolerability of delivering omacetaxine for maintenance in adult patients age 55 and older with acute myelogenous leukemia (AML) in first complete remission following 3 consolidation courses with omacetaxine.

Secondary Objectives:

- To assess the duration of remission.
- To evaluate disease-free survival (DFS).
- To evaluate overall survival (OS).
- To assess for minimal residual disease (MRD) during consolidation and maintenance therapy with omacetaxine.

3. RESEARCH DESIGN AND METHODS:

3.1 Patient Selection:

3.1.1 Inclusion Criteria:

1. Diagnosis of AML including de novo, secondary, or with an antecedent hematologic disorder [AHD] according to the World Health Organization (WHO) criteria²⁵ (**Appendix A**).
2. Age \geq 55 years.
3. Patient eligible for standard induction chemotherapy based on ECOG PS and vital organ function at the discretion of the treating physician.
4. Patients who received 1-2 cycles of hypomethylating therapy (decitabine azacitidine) are eligible.
5. Provide signed written informed consent.
6. Be able to comply with study procedures and follow-up examinations.
7. Be non-fertile or not pregnant or lactating & agree to use birth control during the study through the end of last treatment visit.
8. Adequate renal and hepatic function **at the time of second registration**:
 - a. Total bilirubin \leq 1.5 x institutional Upper Limit of Normal (ULN); and
 - b. Aspartate aminotransferase (AST) and alanine aminotransferase (ALT) \leq 2.5 x ULN; and
 - c. Serum creatinine \leq 1.2 times the upper limit of normal.
9. ECOG performance \leq 2 (**Appendix B**) **at the time of second registration**:
10. Patients with a history of carcinoma in remission, on no therapy or on hormonal therapy for the adjuvant treatment of breast carcinoma or prostate carcinoma are included in the study.

3.1.2 Exclusion Criteria:

1. Diagnosis of acute promyelocytic leukemia (APL, French-American-British [FAB] classification M3 or WHO classification of APL with t (15;17)(q22;q12), (*PML/RARA* and variants).
2. Prior treatment with omacetaxine
3. Relapsed or refractory AML.

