Data quality will be monitored on an ongoing basis by random checks of CRFs following the Leukemia Working Group meetings. Co-investigators and staff will be trained on the conduct of the protocol and any additional training based on protocol amendments at the Hematology/Leukemia multi-disciplinary meetings, which meets regularly. Recording, grading, and reporting of adverse events will be carried out contemporaneously with each patient's clinic visit and will abide by the guidelines provided by the Winship Cancer Institute Clinical Trials Office. Deviations will be added to the Deviation Log, which is updated and reviewed at the Leukemia Working Group meetings.

The Principal investigator is responsible for sending a yearly IND summary report, which includes an update and status of the study and a tabulation of the AEs/ SAEs, as well as status of the study subjects, to the FDA. The PI is also responsible for collecting, reviewing, analyzing and reporting to the FDA and other investigators any potential serious risks that qualify for reporting under the FDA's IND Safety Reporting regulations at 21 CFR §312.32, .64 and 21 CFR § 320.31. In addition, the Sponsor-Investigator must copy the Emory IRB on

any such reports and include an analysis of whether the Sponsor-Investigator believes the event constitutes an Unanticipated Problem Involving Risks to Subjects or Others.

6. STATISTICAL CONSIDERATIONS:

Safety: Target omacetaxine dose is the dose that can be delivered to 70% patients without dose limiting toxicity (DLT) as defined above (section 3.3.4). Safety analysis will be conducted through continuous monitoring of AE/SAE. If 2 of the first 3 patients experience DLT, we stop the trial. After that, we stop the trial if there is evidence that the target probability of DLT exceeds 30% and the probability of falsely stopping the trial is 10% or less. The following table gives the minimum number of DLTs in order to stop the trial and the probability of falsely terminating the trial if in fact the probability of DLT is 30% calculated using the binomial distribution. For example, if after enrolling 6 patients, 4 or more experienced DLT, then we stop the trial and conclude that the target probability of DLT is more than 30%. The probability of incorrectly stopping the trial is 0.07.

To be considered safe, the upper limit of the one-sided 95% CI of DLT among 15 patients must not be greater than 30%.

Number of Patients	3	4	5	6	7	8	9	10	11	12	13	14	15

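### A patient with suspected MDS may start omacetaxine at pre-AML baseline counts, but the stopping rule and the dose table do not consistently accept those counts afterwards

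*Combined protocol and SAP*

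**What the plan says.** Inclusion criterion 1 (3.1.1) is broad: "Diagnosis of AML including de novo, secondary, or with an antecedent hematologic disorder". Patients with pre-existing marrow disease are therefore expected, and four rules deal with their counts.

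- **3.3.1 B, consolidation.** The next cycle requires ANC of at least 1 × 10⁹/L and platelets of at least 100 × 10⁹/L. The exception reads: "Patients with history of or suspected MDS prior to AML who fail to recover their ANC and platelets after induction chemotherapy, may start omacetaxine". The count they must reach is their own pre-AML one.
- **3.3.1 C, maintenance.** The same thresholds apply, with a narrower exception: "Patients with history of MDS prior to AML who fail to recover their ANC and platelets after induction chemotherapy, may start omacetaxine". Suspected MDS is not mentioned.
- **3.3.4 A, dose table.** Adjustments depend on "time to count recovery to < grade 2 hematological toxicity" for WBC/neutrophils and platelets. Anemia is the only stated exemption. In the row beyond 50 days, a marrow is taken and relapse ends participation. A hypoplastic marrow is reassessed after 2 weeks, and the first-action cell ends: "If no recovery 2 weeks post-marrow assessment, patient will be taken off study".
- **3.3.4 D, stopping rules.** Omacetaxine is discontinued if counts have not recovered to the fixed thresholds, "or to baseline ANC and platelets (for patients with history of underlying MDS) after 50 days".

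Section 6 defines DLT by pointing back to 3.3.4. It defines feasibility as 9 delivered cycles in at least two thirds of patients.

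**The concern.** The plan accepts that some patients cannot be expected to exceed the counts they had before AML, and lets them start on that basis. The rules that then govern dose and discontinuation do not carry this through to the same patients. Someone with no net loss of counts can be taken off drug for being at the level that permitted entry, and two investigators following different sections could manage identical patients differently.

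This reaches the analysis in two ways. A patient removed before cycle 9 is a feasibility failure. The removal might also be counted as a DLT, since section 6 relies on 3.3.4 and 3.3.4 labels no event a DLT. With 15 patients, one classification carries weight.

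**Working it through.** The plan gives no figure on this point to reproduce. The first part is a comparison of text; the second is a short illustration.

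**Which rule accepts a pre-AML baseline, and for whom**

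| Rule | Suspected MDS | History of MDS |
|---|---|---|
| 3.3.1 B, starting in consolidation | yes | yes |
| 3.3.1 C, maintenance | no | yes |
| 3.3.4 D, stop after 50 days | no | yes |
| 3.3.4 A, dose table | no | no |

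**Patient 1: suspected MDS, baseline below ANC 1,000/mcL or platelets 100,000/mcL.** The patient starts under 3.3.1 B and returns fully to baseline after cycle 1. Rule D asks for the fixed thresholds, and its baseline alternative does not cover this patient. After 50 days the discontinuation criterion is met.

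**Patient 2: history of MDS, baseline grade 2 or worse.** The patient returns fully to baseline after cycle 1. Rule D is satisfied. Under the 3.3.4 A table the count never resolves to below grade 2. The row for more than 36 and fewer than 50 days describes patients who resolve in that window, so it does not apply and neither does its 20% reduction. Only the row beyond 50 days fits. It calls for a marrow, with three possible findings:

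- Relapse: off study, as it should be.
- Hypoplastic: reassess at 2 weeks, and off study if there is no recovery.
- Neither: no clear instruction. Read literally and alone, the closing sentence would still remove the patient.

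**Before cycle 2.** The 3.3.1 B exception is worded for failure to recover after induction. If it covers only the first start, neither patient can begin cycle 2 at baseline, although rule D would not discontinue patient 2. That 3.3.1 C repeats the allowance for maintenance, after three omacetaxine cycles, suggests a wider intent, but the text does not say so.

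**Feasibility illustration**

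Inputs: 15 consolidation/maintenance patients (Synopsis); 9 cycles in at least 2/3 (section 6). Threshold: 2/3 × 15 = 10. The true delivery rate q is not in the documents; 70% and 80% are assumed.

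- No such patient: P(Bin(15, q) ≥ 10).
- One such patient, certain to fail: the other 14 must supply all 10, so P(Bin(14, q) ≥ 10).

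| q | None affected | One affected | Change |
|---|---|---|---|
| 70% | 0.722 | 0.584 | −0.138 |
| 80% | 0.939 | 0.870 | −0.069 |

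**Safety, only if the removal is scored as a DLT**

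Section 6 requires the one-sided 95% upper limit among 15 patients to be no more than 30%. The exact limit for k DLTs is the 0.95 quantile of Beta(k + 1, 15 − k): 27.9% for k = 1 and 36.3% for k = 2. The criterion therefore tolerates one DLT, and one such scoring would use it up.

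**The case against.** Four arguments on the other side deserve weight.

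**The table is less harsh than it looks.** A reader might infer that any patient at a low baseline is cut by 20% after day 36 and then removed. The documents do not support this. The 20% row covers patients who resolve in that window, and in maintenance its reduced schedule is 3 days, the same as the full schedule. The off-study step follows most naturally from a hypoplastic marrow. Clear discontinuation of a patient at baseline is therefore confined to suspected MDS under rule D. For established MDS, what remains is a conflict of standards and a missing instruction.

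**The safety effect is conditional and generic.** A reader might infer that the primary safety verdict is compromised. Section 3.3.4 does not say that such a removal is a DLT, and using up a one-DLT allowance is what any certain DLT does among 15 patients. That sensitivity comes from the final criterion and the unlabelled DLT definition, which are separate matters.

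**The narrower wording may be deliberate.** Suspected MDS is undefined, and limiting the stopping-rule allowance to established disease is a defensible conservative choice in a safety pilot. It fits poorly, however, with admitting suspected cases at baseline counts in 3.3.1 B.

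**Recording.** Appendix C has no field for pre-AML counts, but it is an eligibility checklist, and section 4 sends data to case report forms that are not shown. It cannot be inferred that the counts go unrecorded.

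**Conclusion.** The rules conflict on their face. For suspected MDS, the count that permits entry can require discontinuation after 50 days. For established MDS with a baseline of grade 2 or worse, rule D and the dose table use different recovery standards, and a marrow that is neither relapsed nor hypoplastic has no clear instruction.

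One discontinued patient costs about 14 percentage points in the chance of meeting feasibility at an assumed 70% delivery rate, and about 7 points at 80%. This assumes 15 evaluable patients, independent outcomes in the other 14, and feasibility judged on the observed proportion. The number of affected patients is not given, only patients whose baselines fall short of the relevant thresholds matter, and with none there is no effect. A DLT consequence is possible but not established. The point justifies a wording correction; it does not show that the safety conclusion would be wrong.

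**What to change.** Make three wording changes:

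1. Use the same population, *history of or suspected MDS*, in 3.3.1 B, 3.3.1 C and 3.3.4 D.
2. State in 3.3.1 B and 3.3.1 C that, for these patients, recovery to the documented pre-AML baseline satisfies the count requirement before every cycle. Without this, a patient covered by the other changes could still be unable to start cycle 2.
3. In the 3.3.4 A table, add for these patients only: *or to documented pre-AML baseline ANC and platelets*.

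The changes need no additional patients, visits or tests. The downside is that some true marrow toxicity could be masked in these few patients. Requiring a documented pre-AML count, and keeping the fixed thresholds for everyone else, limits that risk.
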